8.4 Audit and Inspection

The investigator will permit trial-related monitoring, audits, ethical review, and regulatory inspection(s) at their site, providing direct access to source data/documents.

Sites are requested to notify the Trial Office of any MHRA inspections.

8.5 Notification of Serious Breaches

In accordance with Regulation 29A of the Medicines for Human Use (Clinical Trials) Regulations 2004 and its amendments the sponsor of the trial is responsible for notifying the licensing authority in writing of any serious breach of:

- The conditions and principles of GCP in connection with that trial or;
- The protocol relating to that trial, within 7 days of becoming aware of that breach

For the purposes of this regulation, a "serious breach" is a breach which is likely to effect to a significant degree:

- The safety or physical or mental integrity of the subjects of the trial; or
- The scientific value of the trial

Sites are therefore requested to notify the Trial Office of a suspected trial-related serious breach of GCP and/or the trial protocol. Where the Trial Office is investigating whether or not a serious breach has occurred sites are also requested to cooperate with the Trial Office in providing sufficient information to report the breach to the MHRA where required and in undertaking any corrective and/or preventive action.

9. END OF TRIAL DEFINITION

The end of trial will be 18 months after the last participants' last data capture. This will allow sufficient time for the completion of protocol procedures, data collection and data input, and sample analyses. The Trial Office will notify the REC and MHRA that the trial has ended and will provide them with a summary of the trial report within 12 months of the end of trial.

10.STATISTICAL CONSIDERATIONS

10.1 Definition of Outcome Measures

10.1.1 Primary Outcome Measures

The primary outcome measure is defined in Section 2.2.1.

10.1.2 Secondary Outcome Measures

Secondary outcome measures are defined in Section 2.2.2.

CRCTU-PRT-QCD-001, version 1.0

Page 24 of 40 v6.0, 14-Jul-2021

10.2 Analysis of Outcome Measures

Full details will be specified in a Statistical Analysis Plan but an outline of the analyses methodologies of the primary and secondary outcome measures are provided here.

OCTAVE is a multicentre, prospective observational trial, examining humoral immunogenicity in multiple prospective cohorts of patients with end stage kidney disease, liver disease, cancer, immunemediated rheumatic diseases, and transplant recipients. Joint analysis may be held with other disease datasets as the trial evolves.

Two different groups of research samples are being assessed during the trial: Deep Immunophenotyping Group - each disease cohort will include between 100 and 200 participants; and the Serology Group — each disease cohort will include between 150 and 850 participants. Up to 3,250 participants in total. Samples are being collected following vaccination at 4-6 time points for the Deep Immunophenotyping Group and 1-3 time points for the Serology Group (further details can be found in the Schedule of Events).

The primary and secondary outcomes will be assessed using assays and methods proven to give reliable and reproducible results, allowing for direct comparison of participants data, and removing measurement bias.

Vaccination responses will be assessed against a matched control group of vaccinated healthy participants from the health care workers, care homes, and BAME groups. Matching will be performed using the following factors: age, sex, Body Mass Index and ethnicity (details of the matching methodology can be found in the Statistical Analysis Plan).

Missing data will be presented and appropriate sensitivity analysis will be considered including per protocol analysis and multiple imputation.

Statistical analyses will be performed using appropriate statistical software (e.g. Stata, Stata Inc, Texas, USA).

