6.2 Vaccination

Vaccine will be administered in line with its temporary authorisation under Regulation 174 of the Human Medicines Regulations 2012, the national recommendations, and guidance of the Joint Committee on Vaccination and Immunisation (JCVI) and current standard NHS practice.

The trial will have no influence on the type of vaccine given to the participant but the type of vaccine and the batch number used will be recorded in the Case Report Form (CRF) where possible.

Page 13 of 40 v6.0, 14-Jul-2021

CRCTU-PRT-QCD-001, version 1.0

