6.2.2 Second Vaccination (Booster)

The trial will have no influence on the timing of the delivery of the booster but it is expected that the second dose will be delivered in accordance with national recommendations and the guidance of the JCVI.

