10.2.2 Secondary Outcome Measures

Appropriate summary statistics will be produced (continuous measures via means, medians, standard deviations and ranges, categorical measures with number and proportion in each category). Longitudinal assay data will be analysed using linear mixed effects modelling (parametric and more flexible models may be considered), giving estimates of rate of response (slope) and time point specific estimates. Response estimates (absolute changes) at specific time points will be compared between groups (disease-to-disease and disease-to-control) using two-sample t-tests. Time-to-event data will be analysed using Kaplan-Meier methodology and Cox Proportional-Hazards models where appropriate. Contingency tables, Fisher's Exact and Chi-Square testing will be used to investigate categorical data where applicable. Appropriate data plots will be produced where applicable.

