10.2.3 Planned Subgroup Analyses

These analyses are not powered and as such are for exploratory information. Statistical analyses methods given in Section 11.2.2 will be utilised where appropriate.

- Vaccination response in disease-specific subgroups and comparison to control groups
- Vaccine specific response comparisons in disease and control groups
- The effect of disease-specific medications on vaccination response

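### Healthy controls are matched on age, sex, BMI and ethnicity only, so the disease-to-control contrast is open to confounding by vaccine product, dose interval, prior infection and sampling day

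*Protocol*

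**What the plan says.** Protocol Section 10.2 compares vaccination responses with a "matched control group of vaccinated healthy participants from the health care workers, care homes, and BAME groups". It then gives the matching variables: "Matching will be performed using the following factors: age, sex, Body Mass Index and ethnicity". What it passes on is the method of matching: "details of the matching methodology can be found in the Statistical Analysis Plan".

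For the test, Section 10.2.2 states: "Response estimates (absolute changes) at specific time points will be compared between groups (disease-to-disease and disease-to-control) using two-sample t-tests". Section 10.2.1 also plans disease-to-control comparisons under the primary outcomes, on condition that suitable control data exist. Both sections name linear mixed effects models, with no covariates listed.

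On exposure, Section 6.2 says: "The trial will have no influence on the type of vaccine given to the participant". Section 6.2.2 says: "The trial will have no influence on the timing of the delivery of the booster". The only analysis item that refers to product in relation to controls is in Section 10.2.3: "Vaccine specific response comparisons in disease and control groups". That section describes its analyses as unpowered and exploratory.

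**The concern.** The purpose of a healthy control group here is to show whether vulnerable patients respond less well to vaccination than comparable healthy people. Matching on demographics and body mass removes differences in those four factors. It does nothing about factors that act on the measured antibody or T cell response through the vaccination itself, through earlier infection, or through when the sample was drawn.

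Those factors have no reason to balance by themselves. Patients received whatever the national programme gave them, when it gave it. The controls were recruited by other studies from other populations. Section 3 (Trial Design) bases comparability on shared assay platforms. Shared assays remove measurement differences but not differences in exposure. If the mix of products, the infection history or the sampling day differs between a disease cohort and its controls, the contrast takes in that difference. It may then be reported as an effect of disease or treatment, or it may hide a real one.

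**Working it through.** **Step 1. Is each omitted factor free to vary, and is it handled anywhere in the protocol?**

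| Factor | Free to vary? | Recorded for trial participants? | Named for matching or adjustment? |
|---|---|---|---|
| Vaccine product | Yes: three named products or any other approved one (Sections 3 and 6.1), not chosen by the trial (6.2) | Yes, Vaccination form (Table 2) | No; exploratory subgroup item only (10.2.3) |
| Dose interval | Yes, not set by the trial (6.2.2) | Yes, from the two vaccination dates (Table 2) | No |
| Prior infection | Yes: not an exclusion (3.1); only the clinical-protection outcome is restricted to those without it (2.2.2.1) | Yes, Baseline form (Table 2) and N antibody (2.2.1.1) | No |
| Days from booster to sample | Yes (6.4.1), see Step 2 | Booster date on the Vaccination form; sample collection on its own form (Table 2) | No |

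**Step 2. Sampling window (Section 6.4.1).**

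- Serology Group: 28 − 7 = day 21 to 28 + 56 = day 84, a span of 63 days.
- Deep Immunophenotyping Group: 28 − 3 = day 25 to 28 + 3 = day 31, a span of 6 days.

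With exponential decay, the fold difference between the first and last permitted day is 2^(span / half-life). The half-lives are assumptions; the protocol gives none.

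| Assumed half-life (days) | Serology, 63 days | Deep, 6 days |
|---|---|---|
| 30 | 2^(63/30) = 4.3 | 2^(6/30) = 1.15 |
| 60 | 2^(63/60) = 2.1 | 2^(6/60) = 1.07 |
| 90 | 2^(63/90) = 1.6 | 2^(6/90) = 1.05 |
| 120 | 2^(63/120) = 1.4 | 2^(6/120) = 1.04 |

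These are spreads between single samples at the edges of the window, not biases in a group mean. The bias depends on the difference in mean sampling day between cohort and controls, and the controls' window is not stated. Timing therefore matters for the Serology Group and hardly at all, on the trial side, for the Deep Immunophenotyping Group.

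**Step 3. Bias from product mix.** Suppose there is no disease effect. Let one product give a response R times that of another, and let the share receiving it differ by D between cohort and controls. The difference in mean log response is D × log R, so the spurious geometric mean ratio is R^D. R and D are assumptions; the protocol gives neither.

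- R = 2, D = 0.2: 2^0.2 = 1.15
- R = 5, D = 0.4: 5^0.4 = 1.90
- R = 10, D = 0.6: 10^0.6 = 3.98

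**Step 4. What the t-test would do with it.** Take the bias b = D × log10 R, standard error = SD × √(2/n), a two-sided 5% level and equal groups of n. The rejection probability with no disease effect is Φ(b/SE − 1.96) + Φ(−b/SE − 1.96). The log10 SD of 0.6 is assumed. The values of n are the ends of the planned cohort ranges in Section 10.2 (100 to 200 and 150 to 850).

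| R, D | b | Ratio | n=100 | n=150 | n=200 | n=850 |
|---|---|---|---|---|---|---|
| 1.5, 0.1 | 0.018 | 1.04 | 5.5% | 5.7% | 6.0% | 9.3% |
| 2, 0.2 | 0.060 | 1.15 | 11% | 14% | 17% | 54% |
| 4, 0.4 | 0.241 | 1.74 | 81% | 94% | 98% | 100% |

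For the middle row at n = 100: SE = 0.6 × √(2/100) = 0.085 and b/SE = 0.71, which gives about 11%. Increasing n leaves the ratio unchanged and makes a false finding more likely. With SDs of 0.4 to 0.8, and R up to 4 and D up to 0.4, the rejection rate runs from 5.3% to 100%.

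The protocol has no sample size calculation or control-group assumption of its own to reproduce.

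**The case against.** The strongest reply is that covariate adjustment belongs in the SAP. Section 10.2 calls itself an outline, a matching list is not a covariate list, and mixed models are named alongside the t-test. This stands in part. A reader might infer that the trial will certainly leave these factors unadjusted; the protocol does not show that. But the matching factors themselves are fixed in the protocol, with only the methodology deferred. The test that is named for disease against control adjusts for nothing.

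A reader might also infer that the primary result is at risk. The primary objective is the magnitude of response (Section 2.1.1). Comparison with healthy controls is a secondary objective (2.1.2), and under the primary outcomes it is conditional on available control data. The explicit disease-to-control t-test sits under the secondary measures. The T-SPOT interim assessment makes no control comparison, and disease-to-disease contrasts do not use this matching.

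Prior infection is not ignored. The assay was chosen to distinguish responses to vaccination from responses to infection, and history is recorded. That makes adjustment possible; it does not commit the trial to it. The vaccine-specific subgroup item is a real within-product comparison. To call it unpowered is a weak criticism where no analysis has a formal sample size basis. It is nevertheless exploratory, covers one factor of four, and leaves the overall contrast unchanged.

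Finally, nothing in the documents shows that an imbalance exists, and the mild case in the working is nearly harmless. That is correct, and it limits the claim to a risk that the stated design leaves open.

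**Conclusion.** The point holds as a weakness in what the protocol fixes. Followed as written, the four-factor matching and the unadjusted t-test let differences in product, dose interval, infection history or, in the Serology Group, sampling day pass into the disease-to-control contrast. The documents do not establish that bias has occurred or how large it would be. The range of 1.15 to 4.0 for the spurious geometric mean ratio rests wholly on assumed product ratios (2 to 10) and share imbalances (0.2 to 0.6). It covers product only, and its upper end should not be read as an expected value. A milder assumption (1.5-fold, 10 points) gives 1.04. Because the SAP is not shown and the control contrast is a secondary objective, this is something that should be fixed rather than a defect that invalidates the trial.

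**What to change.** In Section 10.2, add vaccine product and prior-infection status (history or N antibody) to the matching factors, or state that the contrast is stratified by or adjusted for them. Exact matching is not required; adjustment would serve. In Sections 10.2.1 and 10.2.2, estimate the disease-to-control contrast from a regression on log response in place of the unadjusted t-test. It should include dose interval and, above all for the Serology Group, days from booster to sample. Where a disease cohort has no controls for a product, say that the contrast is not supported for that product.

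For trial participants, vaccine type, vaccination dates and prior infection are already on the case report form, so no new collection of these is needed. The control studies must be asked for the same fields plus the sampling date. The trial is not shown to control those studies, so this is more than a change of wording. The statistical price is fewer usable controls and wider intervals where a product is rare in either group.

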10.2.2 Secondary Outcome Measures

Appropriate summary statistics will be produced (continuous measures via means, medians, standard deviations and ranges, categorical measures with number and proportion in each category). Longitudinal assay data will be analysed using linear mixed effects modelling (parametric and more flexible models may be considered), giving estimates of rate of response (slope) and time point specific estimates. Response estimates (absolute changes) at specific time points will be compared between groups (disease-to-disease and disease-to-control) using two-sample t-tests. Time-to-event data will be analysed using Kaplan-Meier methodology and Cox Proportional-Hazards models where appropriate. Contingency tables, Fisher's Exact and Chi-Square testing will be used to investigate categorical data where applicable. Appropriate data plots will be produced where applicable.

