Deep Immunophenotyping Group: between 100 and 200 participants depending on disease cohort will be recruited for full immune response analysis. Serology Group: between 150 and 850 participants depending on disease cohort, for **Sample Size** serology analysis Total: Up to 3250participants Eligible for vaccination by one of the SARS-CoV-2 approved vaccines and: For the Deep Immunophenotyping Group, have not received the second dose of vaccine (booster) o For the Serology Group, have not passed 28 days post booster (within -7/+56 Inclusion Criteria ○ Anticipated life expectancy of \geq 6 months Fall into one (or more) of the five disease cohorts who will meet disease relevant classification, disease state, and staging according to established international standards (refer to protocol for details) Deep Immunophenotyping Group: whole blood, peripheral blood mononuclear cells (PBMC), serum, plasma and saliva will be collected at the following time points: Pre-vaccine, baseline (optional) - may have been collected prior to recruitment to **OCTAVE** 1 day after first vaccination (optional) – tempus and EDTA sample only Pre-booster 28 days post-booster (ideally within +/- 3 days) 6 months post-booster (as close to time point as possible) Sample 12 months after first vaccine dose or prior to third vaccine dose (if applicable), **Collection** whichever is earlier **Serology Group:** serum (as a minimum) collected at the following time points: Pre-vaccine, baseline (optional) – may have been collected prior to recruitment to **OCTAVE** Pre-booster (optional) – any time after first vaccination and before booster 28 days post-booster (within -7/+ 56 days)

Trial Duration

Patients will be recruited over a 6 month period and followed up for 12 months in accordance with standard clinical practice for the relevant disease cohort.

Contacts

Sponsor: University of Birmingham

Chief Investigator: [name], University of Glasgow

OCTAVE Trial Office: Cancer Research UK Clinical Trials Unit (CRCTU), University of Birmingham, [name] ⋈ [contact]

CRCTU-PRT-QCD-001, version 1.0

SCHEDULE OF EVENTS

		Screening	Trial Entry	Baseline ¹ Prior to vaccination Optional	Day 1 After First Vaccination ² Optional	Pre- Booster	Post- Booster ³ 28 days post 2 nd vaccination	6 Months Post Booster ⁴	6 Month Follow-up Seen in accordance with clinical practice ⁵	12 Months ⁶
Eligibility assessment		х								
Consent		х								
Trial entry			х							

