2.2.2 Secondary Outcome

2.2.2.1 Clinical protection

First symptomatic, PCR-proven COVID-19 occurrence from 14 days after first dose of SARS-CoV-2 vaccine in participants without evidence of prior infection with SARS-CoV-2

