3.1 Inclusion Criteria

- 1. Are eligible for vaccination by one of the SARS-CoV-2 vaccines approved by the MHRA administered in accordance with national guidelines and current versions of the applicable information for healthcare professionals (see Section 7.1) and:
 - For the Deep Immunotherapy Group only, have not received the second dose of the vaccine (booster)
 - For the Serology Group only, have not passed the 28 days post booster (-7/+56 days)
- 2. Anticipated life expectancy of 6 months or greater
- 3. Fall into one (or more) of the following patient cohorts who will meet disease relevant classification, disease state, and staging according to established international standards:
 - O Diagnosed with any of the following malignancies:
 - Breast
 - Lung
 - Acute Myeloid Leukaemia
 - Multiple Myeloma
 - Diagnosed with the following rheumatic/inflammatory conditions:
 - Specialist diagnosis of relevant condition

Page 9 of 40 v6.0, 14-Jul-2021

- Established on relevant therapy for ≥ 30 days
- Meet the definitions in any of the following cohorts:
 - Deep Immunophenotyping Group::
 - Methotrexate plus inflammatory arthritis (to include RA, PsA, seronegative arthritis, and spondyloarthritis)
 - TNF inhibitors (any) plus inflammatory arthritis (to include RA, PsA, seronegative arthritis, spondyloarthritis)
 - o Rituximab in patients with AAV
 - Serology Group:
 - Methotrexate plus:
 - inflammatory arthritis (RA, seronegative arthritis and PsA)
 - psoriasis
 - TNF inhibitors (any) plus:
 - inflammatory arthritis (RA, seronegative arthritis, axSpA and PsA)
 - psoriasis
 - Crohn's disease
 - IL-17 inhibitors (any), IL-12/23 inhibitors and IL-23 inhibitors plus:
 - seronegative arthritis (PsA and axSpA)
 - psoriasis
 - IL-6 inhibitors (any) with RA
 - JAK inhibitors (any) with RA
 - Rituximab with RA or AAV
 - Any immune modifying treatment with Systemic Lupus Erythematosus (SLE)
- O Diagnosed with the following chronic renal conditions:
 - End stage kidney disease secondary to any cause
 - Renal transplant following end stage kidney disease
- Diagnosed with the following chronic liver conditions:
 - Liver cirrhosis
 - Liver transplantation
 - Chronic liver disease (of any stage), or gastrointestinal disease on immune suppressive therapy
- Haematopoietic stem cell transplant patients:

CRCTU-PRT-QCD-001, version 1.0

Page 10 of 40 v6.0, 14-Jul-2021

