6.5 Participant Follow-Up

Participants will be followed up in accordance with standard clinical practice for the relevant disease cohort.

Data will be collected retrospectively from clinic records 6 months after the second vaccination and 12 months after first vaccination or at the time or 3rd vaccination (whichever is earlier). Data collected from face-to-face consultations or telephone follow-up calls are acceptable.

Page 17 of 40 v6.0, 14-Jul-2021

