9. DATA COLLECTION

The CRF will be comprised of the forms listed in Table 2.

Page 20 of 40 v6.0, 14-Jul-2021

Table 2: OCTAVE Trial Case Report Form

	Form	Summary of Data Recorded*	Schedule for Submission to Trial Office	
Registration		Minimal identifiers (initials and date of birth)	Complete at trial entry	
Baseline		NHS/CHI/ BSBMT registry ID, hospital number, demographic data (sex, ethnicity), World Health Organisation (WHO) performance status (Appendix 3), body mass index, medical history including comorbidities, disease group specific information (including disease status), details of prior COVID-19 infection, collection of baseline research samples	Within 1 month of trial entry	
Treatment Form	First vaccination Second vaccination	Details of rituximab, corticosteroids, and nonsteroidal anti-inflammatory drugs (NSAIDs) and other disease cohort specific	As soon as possible after relevant vaccination	
Vaccination form	First vaccination	treatments Date of vaccination Type of vaccination Batch number (if known) Planned date of booster (if known)	As soon as possible after relevant vaccination	
	Second vaccination	Date of booster Type of vaccination Batch number (if known)		
Vaccination Adverse Reaction	First vaccination	Details of ARs thought to be related to SARS-CoV-2	As soon as possible after relevant vaccination	
Form	Second vaccination	vaccination	relevant vaccination	
Research San	nple Collection Form	Confirmation of collection of research samples in accordance with the protocol	As soon as possible on collection of research samples	
Follow-up		Survival data, COVID-19 infection data, WHO performance status, disease site specific	Six months post second vaccination (booster) and 12 months post first vaccine or third vaccination	

Page 21 of 40 v6.0, 14-Jul-2021

Form	Summary of Data Recorded*	Schedule for Submission
		to Trial Office
Death	Date and cause of death	Immediately upon notification
Death	Date and cause of death	of participant's death
	Used to notify the Trial Office of	Immediately upon patient
Withdrawal of Consent	the participant's withdrawal from	withdrawal
	the trial	Withdrawai
	Details on deviations from the	Immediately upon discovery of
Deviation Form	protocol not captured elsewhere	a deviation
	on the CRF	a deviation
	Details of any SAE thought to be	No later than 24h after
Serious Adverse Event	related to SARS-CoV-2	
	vaccination	becoming aware of the event

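### If one minus Kaplan-Meier is reported as COVID-19 incidence, it will overstate the proportion infected, because death without COVID-19 is a competing event

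*Protocol*

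**What the plan says.** Protocol Section 2.2.2.1 (Clinical protection) defines the sole secondary outcome: "First symptomatic, PCR-proven COVID-19 occurrence from 14 days after first dose of SARS-CoV-2 vaccine in participants" without evidence of earlier infection. Death is not a component.

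Section 10.2.2 (Secondary Outcome Measures) gives the method: "Time-to-event data will be analysed using Kaplan-Meier methodology and Cox Proportional-Hazards models where appropriate". The same sentence stands in Section 10.2.1. Section 10.2.2 also provides for counts and proportions of categorical measures, and for tests on contingency tables. Section 10.2 describes all of this as an outline: "Full details will be specified in a Statistical Analysis Plan but an outline of the analyses methodologies". The SAP was not available for this review.

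Section 3.1 admits patients with "Anticipated life expectancy of 6 months or greater". The Trial Synopsis says participants are "followed up for 12 months in accordance with standard clinical practice". Section 6.5 ends data capture at 12 months after the first dose, or at a third dose if that comes sooner. Table 2 in Section 9 has a Follow-up form recording "Survival data, COVID-19 infection data, WHO performance status" and a Death form recording "Date and cause of death". The protocol does not say how a death without COVID-19 enters the analysis.

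**The concern.** Kaplan-Meier has two states, event or censored. A participant who dies without COVID-19 has had no event and so is censored, as if the event could still happen later. One minus Kaplan-Meier then estimates the COVID-19 risk in a hypothetical population in which nobody dies of anything else. That is not the proportion of the cohort who develop COVID-19.

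The distinction can matter here because the eligible cohorts range from inflammatory arthritis and psoriasis to lung cancer, acute myeloid leukaemia, cirrhosis, end-stage kidney disease and stem cell transplant or CAR-T recipients. Mortality is likely to differ between them. What is at stake is the absolute breakthrough incidence reported for each cohort, a figure that readers would take as a real-world proportion.

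**Working it through.** **Nothing to reproduce.** The protocol states no COVID-19 incidence, no all-cause mortality and no event count, and Section 10.2.5 says no formal sample size calculation was feasible. The rates below are therefore assumptions.

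**Inputs.** From the protocol: the outcome (Section 2.2.2.1), follow-up to 12 months or to a third dose if earlier (Section 6.5), and Serology cohorts of 150 to 850 (Section 10.2). Assumed: 12-month COVID-19 risk in the absence of death, pc, of 5% or 10%; 12-month mortality without COVID-19, pd, from 2% to 50%; constant, independent hazards.

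**Formulas** (T in years):

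- λc = −ln(1 − pc) and λd = −ln(1 − pd)
- One minus Kaplan-Meier, deaths censored: 1 − exp(−λc·T)
- Cumulative incidence, death competing: λc/(λc + λd) × [1 − exp(−(λc + λd)·T)]

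**Worked case,** pc = 10%, pd = 30%, T = 1. λc = 0.1054 and λd = 0.3567, sum 0.4620. One minus Kaplan-Meier is 10.0%. Cumulative incidence is (0.1054/0.4620) × (1 − 0.9 × 0.7) = 0.2280 × 0.37 = 8.44%. A simulation of one million subjects gave 10.0% and 8.45%.

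**Results at 12 months:**

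| Mortality | COVID-19 10%: 1−KM vs cumulative incidence | Excess (points) | COVID-19 5%: 1−KM vs cumulative incidence | Excess (points) | Relative excess |
|---|---|---|---|---|---|
| 2% | 10.0 vs 9.90 | 0.10 | 5.00 vs 4.95 | 0.05 | about 1% |
| 10% | 10.0 vs 9.50 | 0.50 | 5.00 vs 4.75 | 0.25 | about 5% |
| 20% | 10.0 vs 8.98 | 1.02 | 5.00 vs 4.49 | 0.51 | about 11% |
| 30% | 10.0 vs 8.44 | 1.56 | 5.00 vs 4.21 | 0.79 | about 19% |
| 50% | 10.0 vs 7.26 | 2.74 | 5.00 vs 3.62 | 1.38 | about 38% |

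The relative excess hardly depends on the COVID-19 rate.

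**Shorter follow-up.** With T = 0.5 and pc = 10%, one minus Kaplan-Meier is 5.13%. Cumulative incidence is 5.00% at 10% annual mortality (excess 2.6%) and 4.70% at 30% (excess 9.1%), so the relative bias is about half.

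**Scale against sampling error.** The 95% half-width for a 5% proportion, 1.96·√(0.05 × 0.95/n), is 3.5 points at n = 150 and 1.5 points at n = 850. At that incidence the excess stays below 0.8 points for mortality up to 30%.

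**Comparison between cohorts.** Down the 10% column the COVID-19 hazard is the same in every row, and one minus Kaplan-Meier is the same too. Cumulative incidence falls from 9.90% to 7.26% purely because more participants die first. The two quantities answer different questions: Kaplan-Meier tracks the hazard, cumulative incidence the realised burden.

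**The case against.** The strongest reply is that this is a choice of estimand. The outcome is headed clinical protection. For comparing protection, treating deaths as censored is defensible, and the comparison just made supports this. A reader might infer that Kaplan-Meier makes the sickest cohorts look worse protected. The documents do not support that, and with equal COVID-19 hazards the curves coincide. This part of the reply stands. It does not rescue one minus Kaplan-Meier as a statement of how many participants were infected.

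Second, the sentence is generic, is qualified, states no censoring rule and belongs to an outline that defers to the SAP. A reader might infer that the trial will certainly report inflated incidences. The protocol does not say so, and the SAP could specify otherwise. The point is therefore conditional. Still, Kaplan-Meier is the curve-based method named, and no competing-risk alternative appears beside it.

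Third, Kaplan-Meier is not the only incidence summary on offer. Section 10.2.2 also allows proportions, and a crude proportion with deaths kept in the denominator equals the cumulative incidence when follow-up is otherwise complete. That is correct. However, Section 6.5 lets follow-up end at different times according to the third dose, so an estimator that handles censoring is needed.

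Fourth, the six-month life expectancy is an entry floor. A reader might take it as evidence of high mortality, but it is not. Nor is the excess in percentage points always largest where mortality is highest: 20% COVID-19 with 10% mortality gives 0.98 points, against 0.79 for 5% COVID-19 with 30% mortality. Only the relative excess rises with mortality regardless of the COVID-19 rate.

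**Conclusion.** The point holds for absolute incidence only. If one minus Kaplan-Meier is presented as the cumulative incidence of COVID-19 in a cohort, it is biased upward, and a larger sample does not remove the bias. The sizes found above rest on constant independent hazards and on rates that the protocol does not give. At moderate assumed rates the bias is small beside sampling error; it becomes large only at mortality of around 50% or more. The Cox model with deaths censored still gives a valid cause-specific hazard ratio. This is a worthwhile, inexpensive improvement to a secondary outcome, and it does not show that any stated figure is wrong.

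**What to change.** In Section 10.2.2, and in the SAP to match, state for the COVID-19 outcome:

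- Absolute incidence per cohort is estimated with the Aalen-Johansen estimator. Death without prior symptomatic PCR-proven COVID-19 is the competing event, dated from the Death form, and its cumulative incidence is shown alongside.
- Comparisons of protection between cohorts rest on the Cox model, with its result labelled a cause-specific hazard ratio. They do not rest on differences in cumulative incidence, which falls as mortality rises even when the COVID-19 hazard is unchanged.

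The cost is a few sentences and a standard software routine, with no new data. The downside is slightly lower reported incidences and a short explanation of competing risks in the report.
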